6.8 Safety Analyses

Safety assessments in this study consist of vital signs, 12-lead ECGs, neurological assessments, and AEs. Vital signs, ECGs, and neurological assessments will be serially collected (see Time and Events Schedule of Study Procedures, **Section 9**). Adverse events will be collected from the time of informed consent through to the final Day 30 visit.

6.8.1 Vital Signs

Vitals signs are resting heart rate (bpm), systolic blood pressure (mmHg), diastolic blood pressure (mmHg), temperature (°C), oxygen saturation (%), and respiratory rate (breaths/min). Vital signs will be summarized by treatment group (Group 1), and by surgery type (Group 2) at each assessment timepoint. Summaries will present both observed results by timepoint and change-from-baseline results. Baseline is defined as the last measurement on prior to the end of study drug administration . Baseline statistics will be presented at each assessment timepoint for those subjects reporting data at that timepoint.

Time windows will be derived for each post baseline visit using the time intervals for the study time windows detailed in Table 3.

Study Time	Time Interval for Study Time Window
Baseline	≥ 0 minutes prior to dose
Post-dose 2 hours	1.75 – 2.25 hours after end of study drug administration
Post-dose 4 hours	3.75 – 4.25 hours after end of study drug administration
Post-dose 8 hours	7.5 - 8.5 hours after end of study drug administration
Post-dose 12 hours	11 – 13 hours after end of study drug administration
Post-dose 24 hours	23 – 25 hours after end of study drug administration
Post-dose 36 hours	34 – 38 hours after end of study drug administration
Post-dose 48 hours	46 - 50 hours after end of study drug administration
Post-dose 60 hours	58 - 62 hours after end of study drug administration
Post-dose 72 hours	70 – 74 hours after end of study drug administration
Post-dose 96 hours	92 – 100 hours after end of study drug administration
Day 30	27 – 33 days after end of study drug administration

 Table 3
 Analysis Study Time Windows for Vital Signs Assessments

If there are multiple vital sign values for the same parameter prior to the end of study drug administration, the last value will be chosen for Baseline. If there are multiple vital sign values in a post-end of study drug administration window, the value closest to the target time point will be chosen for analysis. Unscheduled visits can be mapped to a study time only if the scheduled assessment for that time was not done and an unscheduled visit falls into the time interval for the visit window. Data from both scheduled and unscheduled visits will be listed.

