9.2. Duration of the Study and Subject Participation

Participation will begin at the signing of the ICF/obtaining written assent. No more than 30 days should pass between signing of the ICF/obtaining written assent and the administration of study drug. The time from study drug administration till the end of participation is 30 ± 3 days. Therefore, subjects may participate in the study for up to 63 days.

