13.1. Instructions for Conducting Procedures and Measures

All post-dose assessments will be timed from the end of study drug administration.

Day 1 is defined as the day on which study drug is administered. The beginning of surgery is defined as the time of the first incision. The end of surgery is defined as the time of the last suture/staple. Postsurgical is defined as after the end of surgery.

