The study protocol specified that if a cardiac or neurological AE of special interest (AESI) or serious AE (SAE) occurs during the study, if the investigator or medical monitor considers that the event may be related to study treatment or suggests the possible occurrence of local anesthetic systemic toxicity (LAST; with or without the need for treatment [e.g., intralipids]), or if a plausible etiology for the event cannot be found, an unscheduled PK blood sample must be collected and a 12-lead ECG, vital signs, and clinical laboratory tests (hematology and complete metabolic profile [CMP]) according to the study site's standard of care may be conducted. Cardiac and neurological AEs that do not meet one of these three criteria for AESI should be reported and captured in the database as an AE.

Cardiac AESIs include chest pain, abnormal/irregular heart rate, and shortness of breath requiring intervention. Neurologic AESIs include seizure, altered mental status/altered sensorium, rigidity, dysarthria, tremors, tinnitus, visual disturbance, and severe or worsening dizziness (see below). Additionally, the following events may be of special interest if they persist or occur beyond 72 hours post dose: dizziness, hyperesthesia, muscular twitching, and tingling/paresthesia.

Dizziness will be assessed as mild, moderate, or severe based on the National Cancer Institute-Common Terminology Criteria for Adverse Events (NCI-CTCAE) Version 5.0. Mild dizziness is defined as mild

unsteadiness or sensation of movement; moderate dizziness is defined as moderate unsteadiness or sensation of movement limiting instrumental activities of daily living (ADL); and severe dizziness is defined as severe unsteadiness or sensation of movement that limits self-care ADLs. Dizziness will be captured as an AESI if it is severe or worsens or persist beyond 72 hours post dose.

4. **DEFINITIONS**

Study Day

If the date of the event is on or after the date of the end of study drug administration, Study Day is calculated as the date of the event minus the date of the end of study drug administration plus one (1). If the date of the event is before the date of the end of study drug administration, Study Day is the date of the event minus the date of the end of study drug administration.

Treatment-emergent Adverse Events

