Treatment-emergent adverse events (TEAEs) are those with onset on or after the start time of study drug administration, and before or at the end of the study (expected to be Study Day 30 ± 3 days).

Time 0 (zero)

Time 0 is defined as the time of the end of study drug administration, with the exception of AE's and concomitant medications. Time 0 for AE's and concomitant medications are defined as the time of the start of study drug administration.

Time Deviation

For PK sampling time window, *Time Deviation* is the difference (actual – start/end of target window of assessment) between the actual and target window of assessment in the PK sampling. If sampling occurred before the beginning of target window of assessment, time deviation will be calculated by subtracting the actual time from the beginning of the target window of assessment. If the sampling occurred after the end of target window of assessment, time deviation will be calculated by subtracting the actual sampling time from the end of the target window of assessment. Any samples occurring with the target window will have a time deviation of 0.

Baseline

Baseline measurement or assessment is defined as the last available measurement or assessment prior to the start of study drug administration.

Last Follow-up Time

For subjects who withdraw prematurely, the last follow-up time will be defined as the maximum of the last pain or any other study assessment, the last concomitant medication start or end datetime, and the last adverse event start or end datetime.

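### Day 30 is counted in two ways one day apart, so a visit on Study Day 27 that is on schedule under the Day 1 count misses the SAP's Day 30 analysis window

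*SAP*

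**What the plan says.** Some passages count the dosing day as Day 1:

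- Protocol section 13.1: "Day 1 is defined as the day on which study drug is administered". Protocol Table 1 labels its columns D1, D7 and D30 and gives the D30 visit ±3 days.
- SAP section 4 (Definitions) computes Study Day as the date difference from the end of dosing plus one, so the dosing day is Study Day 1.
- SAP section 4 describes the end of study as "expected to be Study Day 30 ± 3 days".

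Other passages count days elapsed since dosing:

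- Protocol section 9.2: "The time from study drug administration till the end of participation is 30 ± 3 days".
- Protocol section 13.1 also says: "All post-dose assessments will be timed from the end of study drug administration". A note under protocol Table 1 is to the same effect.
- SAP Table 3 (section 6.8.1, vital signs) and SAP Table 4 (section 6.8.3, neurological assessments) set Day 30 at "27 – 33 days after end of study drug administration".

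Sections 6.8.1 and 6.8.3 assign post-baseline readings to time points by these tabulated intervals. Neither says what happens to a scheduled reading that falls in no interval. The notes to Listings 16.2-14.1.1 and 16.2-16.1.1 flag out-of-window readings against the Time and Events schedule, not against Tables 3 and 4.

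**The concern.** After 96 hours, Day 30 is the only fixed time point for vital signs and the neurological assessment (hospital discharge is the other, and its timing varies). Change from baseline in vital signs is a protocol safety endpoint, and safety is the secondary objective.

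If a site schedules by the Day 1 count, a visit on Study Day 27 is within its window. The analysis window starts a day later, so that reading would have no Day 30 row to go into. Because the listings take their flag from a different source, the same reading could appear unflagged in a listing and be absent from the matching summary table. At stake are the denominators and completeness of the Day 30 rows, in columns that are small to begin with.

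**Working it through.** **Inputs.** Study Day = date difference + 1 (SAP section 4); visit window Day 30 ± 3 (protocol Table 1; SAP section 4); analysis window 27 to 33 days after the end of dosing (SAP Tables 3 and 4); 30 ± 3 days from dosing (protocol section 9.2).

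**The protocol's own figure.** Section 9.2 concludes: "Therefore, subjects may participate in the study for up to 63 days". Thirty days of screening plus 30 + 3 days gives 30 + 33 = 63 elapsed days, which reproduces it. With the dosing day as Day 1, the span is 30 + (33 − 1) = 62 elapsed days, but 63 calendar days counted inclusively. The 63 therefore does not settle which count was meant.

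**Converting the scales.** Days after dosing = Study Day − 1.

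- Day 30 ± 3 = Study Days 27 to 33 = date differences 26 to 32.
- 27 to 33 days after dosing = Study Days 28 to 34.

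For a date difference d, exact elapsed time lies between d − 1 and d + 1 days, depending on clock times.

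| Study Day | Date difference | Elapsed days | Within Study Day 30 ± 3 | Within 27–33 by date | Within 27–33 by elapsed time |
|---|---|---|---|---|---|
| 27 | 26 | 25–27 | yes | no | never |
| 28 | 27 | 26–28 | yes | yes | depends on clock time |
| 29–33 | 28–32 | 27–33 | yes | yes | always |
| 34 | 33 | 32–34 | no | yes | depends on clock time |

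The two windows differ by one day at each end. Study Day 27 fails the Table 3 and 4 interval however time is measured. Study Day 28 is safe only if days are counted by date, and the SAP does not say whether they are.

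**Size, under assumed visit patterns.** The documents give no distribution of visit days, so these are illustrations for visits spread over Study Days 27 to 33.

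- By date, uniform: 1/7 = 14.3%.
- By date, peaked at Day 30 (weights 1-2-3-4-3-2-1, sum 16): 1/16 = 6.3%.
- By elapsed time, also assuming dosing ends uniformly between 10:00 and 17:00 and visits fall uniformly between 08:00 and 17:00: the chance that a visit is earlier in the day than the end of dosing is (13.5 − 8)/9 = 0.611. The share lost is (1 + 0.611)/7 = 23.0% (uniform) or (1 + 2 × 0.611)/16 = 13.9% (peaked).

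By date, for vital signs with 90 children, this is 90/16 ≈ 6 to 90/7 ≈ 13 readings. Protocol sections 12.3, 13.1.2 and 13.8 restrict the neurological assessment to Part 1. On that base of 45 it is 45/16 ≈ 3 to 45/7 ≈ 6.

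**The case against.** The strongest defence is that Tables 3 and 4 follow the protocol. Section 9.2 gives exactly 27 to 33 days after dosing, and section 13.1 times post-dose assessments from the end of dosing. Read that way, a visit on Study Day 27 is a day early and the SAP is right not to count it as Day 30. This stands as far as it goes: a reader might infer that the SAP contradicts the protocol, but the protocol supports both counts. It does not remove the problem, because the SAP's own Study Day formula and expected end of study use the other count.

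Second, exclusion is an inference. The SAP spells out listing-only handling for PK concentrations (section 6.7.3) and not for vital signs or neurological readings. That is correct. Still, the windowing rule offers no fallback to the nominal visit, so exclusion is its natural reading. A neurological finding might also still be counted in the tabulation at any time after baseline (section 6.8.3).

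Third, a reader might infer that an adverse event on Study Day 34 falls outside the treatment-emergent period. The documents do not support this. The Study Day 30 ± 3 phrase is a parenthetical expectation, and section 6.8.4 runs TEAEs to the final Day 30 visit. An event on Study Day 34 at or before that child's final visit is a TEAE.

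Finally, the percentages depend on assumed visit patterns. The elapsed-time figures further assume minute-level timing for a window written in whole days. Both reservations are fair.

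**Conclusion.** The one-day offset is real and follows from the definitions alone. Readings taken on Study Day 27, on schedule under the Day 1 count, fall outside the Day 30 interval in Tables 3 and 4 and would probably be missing from the Day 30 rows. Some Study Day 28 readings would join them if exact elapsed time were used.

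The number affected is unknown. The 6% to 14% range by date difference assumes visits spread over Study Days 27 to 33, and it would be lower if sites schedule by days since dosing. In Group 1, with 15 + 15 = 30 children per treatment over both parts, the range is about 2 (30/16) to 4 (30/7) readings per column.

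Severity is minor. Only edge-of-window visits in descriptive Day 30 summaries are concerned, the data remain in the listings, and no hypothesis test is affected. Nothing here implies that safety data are lost or that adverse-event counts change.

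**What to change.** In SAP Tables 3 and 4, set the Day 30 window to calendar-date differences of 26 to 33 days after the end of dosing (Study Days 27 to 34), and say that it is counted by date and not by elapsed hours. This keeps every visit allowed under either protocol reading and does not require the SAP to choose between them; reconciling sections 9.2 and 13.1 remains for the sponsor.

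Use the same window for the out-of-window flag on Day 30 readings in the vital-sign and neurological listings, and for the schedule deviation in the Day 30 visit listings (16.2-8.1.3 and 16.2-8.1.4), so that listings and tables agree.

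A 26-to-32-day window would match the Study Day scale but would newly exclude visits 33 days after dosing, which section 9.2 allows, so it is not recommended. The TEAE definition needs no change.

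The cost is one row in each of two SAP tables and a programming note, best made before the tables are programmed. No additional data are needed.

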6.8.2 Electrocardiograms

Investigators will classify ECG tracings as 'normal, 'abnormal not clinically significant' or 'abnormal clinically significant'. ECGs are assessed only at screening or on Day 1 prior to surgery, and a listing of ECG data will be provided.

6.8.3 Neurological Assessments

Neurological assessments include orientation (orientated, disoriented, not assessable), numbness (of lips, tongue, or around mouth), metallic taste, hearing problems, vision problems, and muscle twitching. The number and percentage of subjects will be tabulated for each neurological assessment by treatment group for Group 1 and by surgery type for Group 2, at any time after baseline and at each assessment timepoint.

Time windows will be derived for each post baseline visit using the time intervals for the study time windows detailed in Table 4.

Study Time	Time Interval for Study Time Window
Baseline	≥ 0 minutes prior to dose
Post-dose 2 hours	1.75 – 2.25 hours after end of study drug administration
Post-dose 4 hours	3.75 – 4.25 hours after end of study drug administration
Post-dose 8 hours	7.5 – 8.5 hours after end of study drug administration
Post-dose 12 hours	11 – 13 hours after end of study drug administration
Post-dose 24 hours	23 – 25 hours after end of study drug administration
Post-dose 36 hours	34 – 38 hours after end of study drug administration
Post-dose 48 hours	46 – 50 hours after end of study drug administration
Post-dose 60 hours	58 – 62 hours after end of study drug administration
Post-dose 72 hours	70 – 74 hours after end of study drug administration
Post-dose 96 hours	92 – 100 hours after end of study drug administration
Day 30	27 – 33 days after end of study drug administration

Table 4Analysis Study Time Windows for Neurological Assessments

If there are multiple neurological assessment values for the same parameter prior to the end of study drug administration, the last value will be chosen for Baseline. If there are multiple neurological assessment values in a post-end of study drug administration window, the value closest to the target time point will be chosen for analysis. Unscheduled visits can be mapped to a study time only if the scheduled assessment for that time was not done and an unscheduled visit falls into the time interval for the visit window. Data from both scheduled and unscheduled visits will be listed.

6.8.4 Adverse Events

Adverse events will be coded using the Medical Dictionary for Regulatory Activities (MedDRA).

An AE will be considered TEAE if the onset date and time is between the start time of study drug administration and the final Day 30 visit.

If an AE has a partial onset date and time the imputed start and stop dates and times will be used to determine treatment-emergence (e.g., stop date and time is before start time of study drug administration). All AE summaries will present TEAEs only; AEs that are not treatment-emergent will be included in listings but not summarized.

The incidence of subjects reporting TEAEs will be tabulated by the number and percentage of subjects reporting the TEAE. Incidence is defined as a subject reporting at least one TEAE within the summary level. Summary levels are 'at least one TEAE', System Organ Class (SOC) and Preferred Term. Subjects will be counted only once within each reporting level on the table. For example, if a subject reports a TEAE of headache on two separate occasions, the subject will be counted only once in the headache row of the table. Similarly, if a subject reports two separate TEAEs within the same SOC the subject will only be counted once in the summary row for that SOC. A summary of subjects reporting at least one TEAE during the study will also be presented.

The first row on every TEAE table will be the number and percentage of subjects reporting at least one TEAE. Subsequent rows will be presented in descending order of subject counts for the overall within each age group and treatment group, with the most common system organ class first, followed within each SOC by the PT in descending subject count order. For tables presenting the severity or relationship to study treatment of AE, the sort order will be determined by the number and percentage of subjects reporting the PT, thus the sort order of rows will remain the same for the relation or severity tables as the tables by preferred term.

The following summaries will be presented for the AEs reported by the subjects:

An overview of all TEAEs, serious TEAEs and TEAEs of Special Interest will present the number and percentage of subjects in the following categories:

- Any TEAE
 - Maximum severity: Mild
 - o Maximum severity: Moderate
 - Maximum severity: Severe
- At least one related TEAE
- At least one serious TEAE
- At least one TEAE of special interest
- Subjects discontinued due to a TEAE
- Died on study (i.e., within 30 days of study drug administration)

Subjects will be counted once in each of the above categories except for maximum severity. Subjects will be counted only once at the highest severity reported. For example, if a subject has a mild and severe headache and a moderate rash, the subject will be counted under maximum severity of severe only.

Adverse event tables will present the data within each age group of the study. Incidence tables will be created for the following groups of TEAEs:

- All TEAEs by System Organ Class (SOC) and Preferred term (PT) sorted in descending order of frequency
- All TEAEs by relationship to study drug
- All TEAEs by severity
- All TEAEs of special interest
- All serious TEAEs

If there are no AEs to report on any of the above tables, the table should be created with the line 'no adverse events were reported' in the body of the table.

Adverse events will be considered related if the investigator assessment of relationship to study treatment is either 'possible', 'probable' or 'definite'. Adverse events will be considered unrelated if the

investigator assessment of relationship to study treatment is either 'unrelated', 'unlikely related'. All AE summaries based on related AEs will be produced based on the investigator assessment of relatedness.

Table 5 are the MedDRA terms for the adverse events of special interest according to the protocol. All AEs reported by investigators are based on this definition along with their clinical judgement.

		MedDRA 21.1 Dictionary Terms		
Group	Protocol term	Term Level	Term	
	Chest pain	Preferred term	Chest Pain	
Cardiac	Abnormal/irregular heart rate	Preferred term	Heart Rate Irregular	
	Shortness of breath requiring intervention	Preferred term	Dyspnoea	
	Seizure	Preferred term	Seizure	
	Altered mental status	Preferred term	Mental Status Changes	
	Altered sensorium	Preferred term	Depressed level of consciousness	
	Rigidity	Preferred term	Muscle Rigidity	
Neurologic	Dysarthria	Preferred term	Dysarthria	
	Tremors	Preferred term	Tremor	
	Tinnitus	Preferred term	Tinnitus	
	Visual disturbance	Preferred term	Visual Impairment	
	Dizziness*	Preferred term	Dizziness	
	Dizziness [#]	Preferred term	Dizziness	
	Hyperesthesia [#]	Preferred term	Hyperaesthesia	
Other	Muscular twitching [#]	Preferred term	Muscle Twitching	
	Tingling [#]	Preferred term	Paresthesia	
	Paresthesia [#]	Preferred term	Paresthesia	

Table 5. MedDRA Terms for AEs of Special Interest

A listing of the mapping of the system organ class and preferred terms to verbatim terms will be presented.

6.8.5 Laboratory Parameters

Clinical laboratory assessments (hematology, chemistry, and urinalysis) are collected at screening, baseline (prior to the end of study drug administration) and 96 hours after the end of study drug administration. Laboratory results will be summarized by treatment group (Group 1), and by type of surgery (Group 2) at each assessment timepoint. Summaries will present both actual and change-from-baseline results. Baseline statistics will be presented at each assessment timepoint for those subjects reporting data at that timepoint.

Tabulations of the number and percentage of subjects with value of below normal, normal, or above normal will be provided by treatment group (Group 1), and type of surgery (Group 2), at each assessment timepoint.

Time windows will be derived for each post baseline visit using the time intervals for the study time windows detailed in Table 6

Study Time	Time Interval for Study Time Window
Baseline	≥ 0 minutes prior to dose
Post-dose 96 hours	92 – 100 hours after end of study drug administration

 Table 6
 Analysis Study Time Windows for Clinical Laboratory Assessments

If there are multiple clinical laboratory assessment values for the same parameter prior to the end of study drug administration, the last value will be chosen for Baseline. If there are multiple clinical laboratory assessment values in a post-end of study drug administration window, the value closest to the target time point will be chosen for analysis. Unscheduled visits can be mapped to a study time only if the scheduled assessment for that time was not done and an unscheduled visit falls into the time interval for the visit window. Data from both scheduled and unscheduled visits will be listed.

